**The study will be performed over 7 sessions for MCI participants in the 5 Day Intervention (Figure 1):**

- **Visit 1 (Screening and Baseline visit):** This will occur ~1-2 weeks before the Five Day Intervention. The purpose of this visit is to obtain informed consent for the study, to screen participants for inclusion and exclusion criteria, and obtain baseline performance of the participant's NIH Toolbox Cognition Battery and CogState Brief Battery (One Card Learning and One Back Test). The TMS/tDCS Adult Safety Screen questionnaire, Edinburgh handedness assessment, and the PHQ-8 will also be administered.
- **Visits 2-6 (Five Day Intervention Days 1-5):** During these visits the participant will receive either active tDCS or sham stimulation. The CogState Brief Battery (One Card Learning and One Back Test) will be administered during stimulation. The visits will take place during a 1-week period (Day 1-5 corresponds to visits 2-6), as five consecutive visits (Monday-Friday). An Adverse Event questionnaire will be administered after each visit. On Visit 5 (last day of intervention), all participants will complete the NIH Toolbox Cognition Battery testing after stimulation.
- **Visit 7 (One month after completion of intervention) follow up visit:** Participants will undergo final NIH Toolbox Cognition Battery. A questionnaire for blind assessment will also be completed.

Study Schedule: 1-Day MCI and CU	Estimated Time	Pre-Intervention	Intervention	Post-Intervention
Informed Consent	1 hour	x		
Eligibility Checklist 	10 minutes	x		
Adverse Event Monitoring	5 minutes		x	
NIH Toolbox: Cognitive Battery 	30 minutes	x		x 
CogState Brief Battery  (Simultaneous with intervention)	15 minutes		x	
Intervention: 1.5mA tDCS	15 minutes		x	

1. Eligibility checklist includes review of inclusion/exclusion criteria, the Montreal Cognitive Assessment (MoCA) >26 (for CU group only), the modified TMS/tDCS Adult Safety Screen questionnaire, Edinburgh handedness inventory, and PHQ-8 questionnaire

2. NIH Toolbox Cognitive Battery includes: NIH Toolbox Picture Vocabulary Test, Flanker Inhibitory Control and Attention Test, List Sorting Working Memory Test, Dimensional Card Sort Test, Pattern Comparison Processing Speed Test, Picture Sequence Memory Test, Oral Reading Recognition Test

3. NIH Toolbox: Cognitive Battery will be administered 5 minutes after stimulation

4. CogState Brief Battery will be administered while active or sham stimulation occurs

For participants in the 1 day session (MCI and CU) (Figure 2), one visit will include a screening/baseline assessment to screen participants who inclusion and exclusion criteria, and to obtain baseline performance with the NIH Toolbox. The TMS/tDCS Adult Safety Screen questionnaire, Edinburgh handedness assessment, and the PHQ-8 will also be administered, as well as the Montreal Cognitive Assessment (MoCA) >26 for CU participants. Following that, a 15 minute tDCS treatment (active or sham) will be administered and after a rest break, the same assessment using the NIH Toolbox will be repeated. During the tDCS treatment, the participant will do the CogState Brief Battery (One Card Learning and One Back Test). An adverse event questionnaire will be administered after the stimulation.

Risks and Adverse Events: For a full list of risks, see **Appendix C** for more information on anticipated risks. A symptom-based questionnaire will be used to measure adverse events and will be administered at each visit after the screening visit. The frequency and percentage of adverse events will be compared between the 2 treatment arms. Comparisons between arms will be made by using either the Chi-square or the Fisher's exact test.

Safety Evaluation: A literature review showed that all tDCS trials between 1998-2010 [22] showed that of the 209 studies, similar rates in frequency of adverse events in the active vs. sham arms were observed. The most common AE were headache, itching, burning, discomfort and tingling, occurring in 10-40% of patients regardless of treatment group. Refer to **Appendix D** for the Data and Safety Monitoring Plan.

Efficacy Evaluation: The primary outcome measurement is the NIH Toolbox Cognition Battery either at 1 month after intervention (MCI) or after 1 tDCS session (CU and MCI) as compared to baseline scores.

Expected outcomes: We anticipate a change in the NIH Toolbox Cognition Battery scores in the 1-month follow up scores (MCI) or after 1 tDCS session (CU and MCI) as compared to baseline and do not anticipate any change in the sham group.

Statistical analysis: Continuous variables will be summarized as a mean  $\pm$  SD or median. Categorical variables will be summarized using number and percentage. Univariate descriptive statistics and frequency distributions

will be calculated as appropriate for all variables. Stratified analysis for age in deciles and sex will also be performed. Comparisons between sham and active tDCS (between group comparisons) will be made by one-way Analysis of Covariance (ANCOVA) method to compare the post-intervention test scores between active tDCS group and sham group and adjusting for their baseline (pre-intervention) scores for the NIH Toolbox Cognition Battery. Paired t-tests will be used for within groups for ADAS-cog scores. For analysis of the NIH Cognition Battery, the same method (ANCOVA, paired t-test) will be used. NIH Toolbox Cognition Battery has six subdomains: Executive Function (NIH Toolbox Flanker Inhibitory Control and Attention Test, NIH Toolbox Dimensional Change Card Sort Test), Attention (NIH Toolbox Flanker Inhibitory Control and Attention Test), Episodic Memory (NIH Toolbox Picture Sequence Memory Test, NIH Toolbox Auditory Verbal Learning test), Language (NIH Toolbox Picture Vocabulary Test, NIH Toolbox Oral Reading Recognition Test), Processing Speed (NIH Toolbox Pattern Comparison Processing Speed Test, NIH Toolbox Oral Symbol Digit Test), Working Memory (NIH Toolbox List Sorting Working Memory Test). Each subdomain separately, in addition to the NIH Toolbox Cognitive Function Composite Score, will be computed using the Fully Adjusted Scale score adjusted to normative data. CogState Brief Battery (One Card Learning and One Back Test) will not be included in statistical analysis. Statistical significance will be accepted for two-sided p-values less than 0.05. To control for multiple comparison issues, pairwise comparisons p-values between the groups will be adjusted using the false discovery rate method.

Potential pitfalls & alternative approaches: *Enrollment:* We may be unable to fulfill the planned enrollment schedule of 44 MCI participants within 1 year. If we see enrollment not achieved by Year 1, we will extend the study to Year 2 and consider alternative recruitment strategies (addition of remuneration, etc). *MCI evolution:* Not everyone diagnosed with MCI will go on to develop dementia, and not everyone who develops dementia will develop AD dementia. It is possible brain pathology will have different underlying components (beta amyloid, tau, alpha-synuclein) in participants. Therefore, the MCI group is heterogeneous at best. It should be recognized that there might be a direct interaction between pathology and the subsequent treatment response. *Feasibility:* This is a pilot study to determine feasibility and collect requisite pilot data for grant applications.

Data management: All participant material will be de-identified and stored in a locked cabinet. Any electronically recorded data will be stored on a password-protected hard-drive on a secured, study-specific computer. A Microsoft Excel database will be developed to record data. All data will be double entered. A comparison will be run between the primary and secondary entries to detect inconsistencies and data entry errors. The data will be checked item-by-item against the raw data, and random errors will be corrected. When systematic errors are found, data entry will stop and the data management system will be evaluated. All investigators have completed required training by IRB. Confidentiality will be protected through the use of study identification numbers that will be kept separate from personal identifiers. All study documents will be kept in locked file cabinets in the Collaborative Research Building at Mayo Clinic in Arizona. All study materials will identify participants solely by the assigned code numbers. We will take all necessary steps to protect the confidentiality of all data and computer records.

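### In the 1-day cohorts the NIH Toolbox is repeated about 50 minutes after it first began, with no alternate forms or allowance for practice, which blurs the Episodic Memory result and undermines the within-arm paired t-tests

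*Combined protocol and SAP*

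**What the plan says.** The paragraph on the 1-day session, below the table Study Schedule: 1-Day MCI and CU, puts everything in a single attendance: "one visit will include a screening/baseline assessment", then "a 15 minute tDCS treatment (active or sham) will be administered". The retest comes later in that attendance: "after a rest break, the same assessment using the NIH Toolbox will be repeated". Footnote 3 to that table fixes the delay: "NIH Toolbox: Cognitive Battery will be administered 5 minutes after stimulation". The table estimates 30 minutes for the battery and 15 for stimulation.

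Footnote 2 lists seven tests, ending with "Pattern Comparison Processing Speed Test, Picture Sequence Memory Test, Oral Reading Recognition Test". It gives no form or version for any of them. The Statistical analysis section builds one subdomain as "Episodic Memory (NIH Toolbox Picture Sequence Memory Test, NIH Toolbox Auditory Verbal Learning test"; the second of those tests is not in the administered list.

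Efficacy Evaluation makes the whole battery primary: "The primary outcome measurement is the NIH Toolbox Cognition Battery either at 1 month after intervention (MCI) or after 1 tDCS session (CU and MCI". Each subdomain is analysed separately, alongside a composite. Arms are compared by ANCOVA adjusted for baseline, and both the synopsis and the Statistical analysis section add paired t-tests within arm. Under Expected outcomes the investigators "do not anticipate any change in the sham group".

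**The concern.** People tend to score better on a cognitive test the second time. With a short interval they may also remember its content. Picture Sequence Memory and List Sorting are, judging by their names and purpose, the two administered tests where remembered content seems most likely to help.

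Two things are at stake. The first is interpretation. Stimulation falls between first exposure and retest. If the content is the same, an active-sham difference in Episodic Memory could arise from better or worse holding of material learned before stimulation, and it would still be reported as an answer to Aim 2, which asks about cognition after one session. The second is the within-arm analysis. A paired t-test attributes any before-after change to the intervention, and the plan's expectation for sham leaves no room for a retest gain. The 1-day cohorts hold 44 + 44 = 88 of the 132 planned participants.

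**Working it through.** **Interval.** Inputs from the 1-day schedule: battery 30 minutes, stimulation 15, wait 5.
- Start of first battery to start of second: 30 + 15 + 5 = 50 minutes.
- End of first to start of second: 15 + 5 = 20 minutes.

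These are lower figures. Electrode set-up adds time. The 1-day paragraph also names the safety screen, handedness test, PHQ-8 and MoCA after the baseline battery and before treatment; if they are done in that order, both gaps grow.

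**The plan's own power figure.** Inputs from Power and Sample Size Calculation: d = 0.60, 19 per arm, alpha 0.05, ANCOVA, 70% power. The pre-post correlation r is not stated. The residual variance is 1 − r², the noncentrality is d/√(1 − r²) × √(n/2), and df = 38 − 3 = 35.
- With r = 0 (df kept at 35), power is about 44%.
- With r = 0.69, 1 − r² = 0.524 and √0.524 = 0.724. The noncentrality is 0.60/0.724 × √9.5 = 2.55, and power is 70%.

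So r = 0.69 is the value that reproduces the plan's figure. It is used below as an assumption.

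**ANCOVA under a common retest gain.** Write the second score as performance after stimulation (P) plus a retest contribution (K). The expected arm difference is ΔP + ΔK. If K has the same mean in both arms, ΔK = 0 and the contrast is unbiased. A simulation with no treatment effect (20,000 replicates, 19 per arm, r = 0.67) agrees: for common gains of 0.2 to 0.8 SD, ANCOVA rejects about 5% of the time and the mean estimate is about 0. If stimulation alters retention of the first sitting's content, ΔK is not zero. Randomisation does not remove it, and the score cannot separate it from ΔP.

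**Paired t-test under the same gain, no treatment effect.** With unit variances the SD of change is √(2(1 − r)) = √0.62 = 0.787 at r = 0.69. The noncentrality is gain/0.787 × √19, with df = 18.

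| Assumed gain (SD) | Noncentrality | Chance of p < 0.05, r = 0.69 | Same, r from 0.5 to 0.8 |
|---|---|---|---|
| 0.3 | 1.66 | 35% | 24% to 50% |
| 0.5 | 2.77 | 74% | 54% to 90% |

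This applies to each arm separately, sham included. The documents give no retest figures, so the gains are assumptions.

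**Power of the ANCOVA.** If individual gains vary with SD s, independent of baseline, the residual variance becomes 0.524 + s². At s = 0.2 this is 0.564 and power is 67%; at s = 0.5 it is 0.774 and power is 53%. If scores are capped at 1.0 SD above the baseline mean, a gain of 0.3 to 0.5 SD lowers the simulated effect from 0.45 to 0.39–0.34. With a cap at 2.0 SD, a gain of 0.5 SD lowers it only from 0.57 to 0.53.

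**The case against.** The strongest reply is that the documents never say identical items are reused. The wording can mean the same battery in another form, since tests are listed by name only. A reader might infer that the post-stimulation Episodic Memory score does measure recall of earlier material. The text does not establish that; it shows only that the form is unspecified at a short interval. This stands, and the point is therefore conditional.

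Second, the main comparison is randomised 1:1 and baseline-adjusted. A reader might infer that practice biases the active-sham contrast. A common gain does not, as shown above. A difference in retention would also be a genuine cognitive difference between arms. This too stands: the between-arm problem is one of naming the effect, in one of six subdomains, in a pilot. It does not rescue the paired tests.

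Third, a reader might take the power losses as findings. They are not. The correlation of 0.69 is solved back from the stated power, and a correlation between two sittings would already contain variation in retest gain. Adding s² may therefore count it twice; at s = 0.5 the residual variance rises by 0.774/0.524 − 1 = 48%. The ceilings are also assumed: the plan uses normatively adjusted scores and states no maximum, and a higher cap costs little.

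**Conclusion.** The point holds in a limited form. As written, the protocol repeats the battery about 50 minutes after it first began, by estimated times, and makes no provision for alternate forms or practice. If content is reused, the Picture Sequence Memory result, and possibly List Sorting, is open to two explanations that the data cannot separate. No administered test offsets this within Episodic Memory, because the other test named for that subdomain is not scheduled.

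The clearest quantitative consequence is for the within-arm tests: about 35% to 74% significant with no treatment effect, assuming 19 per arm, r = 0.69 and a gain of 0.3 to 0.5 SD. The expectation of no change under sham fails under the same conditions. Any loss of power in the ANCOVA is speculative, and the documents do not support a figure for it.

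**What to change.** In the 1-day paragraph, state that the second battery uses a different form of Picture Sequence Memory, and of List Sorting if one exists, with form order counterbalanced within arm. The documents do not say whether such forms exist; that is an assumption to check first. If alternate forms are already intended, a sentence saying so is enough.

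In the Statistical analysis section and the synopsis, base efficacy conclusions for the 1-day cohorts on the active-versus-sham ANCOVA and label the paired t-tests descriptive. Under Expected outcomes, allow for a retest gain in sham. For any test without a second form, state in advance that its 1-day result may reflect retention of material learned before stimulation.

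The cost is a few sentences and a form-order list tied to the randomisation schedule, with no extra visits, tests or participants. The downside is a little added noise from differences in form difficulty; counterbalancing keeps this out of the arm comparison. Rotating forms in the 5-day cohort as well is optional: its baseline is one to two weeks before treatment and its primary assessment one month after, and nothing here shows a need for it.

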Cathodal Transcranial Direct  
Current Stimulation (tDCS) in  
Mild Cognitive Impairment  
(MCI): A Randomized, Double-  
Blind, Sham-Controlled Pilot  
Study

NCT# 03521089

July 19, 2017

**Cathodal Transcranial Direct Current Stimulation (tDCS) in Mild Cognitive Impairment (MCI): A Randomized, Double-Blind, Sham-Controlled Pilot Study**

**Principal Investigator:** [name], MSc (Advisor/Primary Mentor)

**PhD Candidate:** [name]

**Co-investigators:** [name], DO, MS; [name]; [name]; [name]; [name]; [name]; [name]; [name], PhD

Title	Cathodal Transcranial Direct Current Stimulation (tDCS) in Mild Cognitive Impairment (MCI): A Randomized, Double-Blind, Sham-Controlled Pilot Study
IRB Protocol Number	16-007478
Phase	Pilot
Study Design	Randomized (1:1), double-blind, sham-controlled
Overall Study Duration	12 months
Participant Participation Duration	8 weeks
Objectives	
 
(1) To compare the effects of cathodal tDCS applied to the right dorsolateral prefrontal cortex (DLPFC) on cognitive outcomes as measured by the NIH Toolbox Cognition Battery 1-month post treatment as compared to baseline in participants with MCI.
 
(2) To compare the effects of cathodal tDCS applied to the right dorsolateral prefrontal cortex (DLPFC) on cognitive outcomes as measured by the NIH Toolbox after 1 session of tDCS in participants who are cognitively unimpaired (CU).
 
(3) To compare the effects of cathodal tDCS applied to the right dorsolateral prefrontal cortex (DLPFC) on cognitive outcomes as measured by the NIH Toolbox after 1 session of tDCS in participants who have MCI.
 

Number of Participants	44 MCI participants in 5 day intervention: 22 in each arm (active vs sham); 44 CU participants in the 1 day intervention: 22 in each arm (active vs sham); 44 MCI participants in the 1 day intervention: 22 in each arm (active vs sham)
Diagnosis and Main Inclusion Criteria	Diagnosis of mild cognitive impairment or cognitively unimpaired healthy elderly (verified by the Montreal Cognitive Assessment), male/female aged 55-85, right handed
Study Device	Soterix Medical 1x1 Low Intensity Transcranial Electric Stimulator (tES) Model 2001: Stimulates cerebral cortex at low intensity (up to 2mA) resulting in changes in cortical excitability and neural plasticity

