### Other potential side effects of tDCS that may be experienced *during* treatment

- **Skin Irritation:** There is a risk of mild skin irritation at the location where the electrode sensors have been placed, but this usually consists of minor redness that will go away quickly after they are removed. Localized tingling sensation, itching, skin erythema, scalp discomfort, and burning sensations have also been reported equally in active and sham tDCS and resolve after treatment.
- **Headache:** A mild headache can occur following tDCS treatment that usually resolves soon after the procedure. We will try to reduce the risk of headache by assuring the participant’s comfort before and during the procedures.

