### Other potential side effects that may be experienced *following* rTMS treatment

Transient redness under the electrode, local pain, headache including migraine, transient dizziness, brief changes in attention and thinking). **Severe depression:** If a participant states they are severely depressed during the trial, we will promptly refer them to Arizona’s Psychiatry and Psychology department. This will be facilitated through [name] (PI) and [name], who are members of the department of psychiatry and psychology and part of the research team.

Treatment plan for other potential side effects experienced *following* treatment:

Participants reporting headaches during or following study treatment will be encouraged to take acetaminophen or ibuprofen prior to the daily treatment. All patients will be monitored, and appropriate treatment will be recommended including the possibility of stopping tDCS. All symptomatic interventions will be recorded in participant's case file.

Device-Related Adverse Event

A device related adverse event is defined as any adverse event for which, at least, a reasonable possibility exists between the event and the investigational device (e.g., the relationship between the device and event cannot be ruled out).

Device Failure, Malfunctions and Near Incidents

Investigators will report all possible device failures, malfunctions or near incidents observed during the course of the trial. These incidents will be documented as follows:

**Device Failure:** A device failure has occurred when the device is used in compliance with the study protocol, but does not perform as described in device manual and also negatively impacts treatment of the study participant.

**Device Malfunction:** A device malfunction occurs when an unexpected change to the device that is contradictory to the device manual is observed, which may or may not affect device performance.

**Device Misuse:** Any use of the investigational device by an investigator that is contradictory to the application described in the study protocol will be categorized as device misuse.

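### In the two 1-day cohorts (88 of 132 participants) the only scheduled adverse-event questionnaire is tied to stimulation and nothing is collected after the single visit, so later-starting effects would be under-counted in both arms

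*Combined protocol and SAP*

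**What the plan says.** The text below the 1-day schedule describes one visit: screening and baseline testing, 15 minutes of active or sham tDCS, a rest break, then the repeat NIH Toolbox. On adverse events it says: "An adverse event questionnaire will be administered after the stimulation". In the 1-day schedule table, the adverse-event row (5 minutes) is marked under Intervention only. The repeat Toolbox (30 minutes) is marked under Post-Intervention, with the footnote "NIH Toolbox: Cognitive Battery will be administered 5 minutes after stimulation".

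For the 5-day cohort, the description of Visits 2-6 says: "An Adverse Event questionnaire will be administered after each visit". The paragraph on Risks and Adverse Events sets a general rule that the questionnaire is given at every visit that follows screening. It also plans a comparison of adverse-event counts and percentages between the two arms by Chi-square or Fisher's exact test.

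Appendix C separates effects felt during treatment from effects that follow it. The second list (whose heading says rTMS) reads: "Transient redness under the electrode, local pain, headache including migraine, transient dizziness, brief changes in attention and thinking". Under effects during treatment it adds: "A mild headache can occur following tDCS treatment that usually resolves soon after the procedure". Item 1 (Participant Safety) of the Data and Safety Monitoring Plan says that participants are watched for adverse events for the whole of each visit.

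**The concern.** The document expects some effects to appear after the session, yet for two of its three cohorts it schedules one structured question, linked to stimulation, and then has no further contact. The general rule cannot fill the gap, because it counts visits after screening and these participants' only visit includes screening. Appendix C's plan for headaches after treatment refers to daily sessions and so assumes that participants return; the 1-day participants do not.

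What is at stake is the safety description that this pilot is meant to supply for later grant applications. A low rate of after-effects in the 1-day cohorts would partly reflect when the question was asked. Because the place of the questionnaire relative to the Toolbox is open, staff could also give it at different times to different participants, and the observation window would then vary.

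**Working it through.** **Number affected.** The synopsis lists three cohorts: MCI on the 5-day schedule, CU on the 1-day schedule, and MCI on the 1-day schedule. Each has 22 active and 22 sham, so 22 + 22 = 44. The total is 3 × 44 = 132 and the 1-day total is 2 × 44 = 88, so 88/132 = 66.7%. Across the two 1-day cohorts there are 44 per arm.

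**When the question is asked.** Two readings of the 1-day text are possible.

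- *Before the repeat Toolbox.* The adverse-event mark sits under Intervention and the Toolbox mark under Post-Intervention. A 5-minute questionnaire would fit the 5-minute gap.
- *After the repeat Toolbox.* The sentence on the questionnaire comes after the sentence on the Toolbox, and a questionnaire at the end of the visit would also be after stimulation. Sentence order does not settle it, since the CogState test, which runs during stimulation, is also described after the Toolbox.

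The two readings differ by about 5 + 30 = 35 minutes. No sentence chooses between them.

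**What each source of data covers in the 1-day cohorts.**

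| Onset of the effect | Questionnaire | General monitoring | Later contact |
|---|---|---|---|
| By the time of the questionnaire | Yes | Yes | – |
| Later in the visit | No | Yes, but not said to enter the arm comparison | – |
| After leaving | No | No | None described |

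**Possible size, using headache as an illustration.** Appendix C cites headache in 14.8% of those on active tDCS and reports no difference in adverse-event rates from sham. Assume 14.8% in both arms. Expected headaches are 88 × 0.148 = 13.0, or 44 × 0.148 = 6.5 per arm. Let f be the share that starts after the questionnaire. The documents give no value for f, so the whole range is shown.

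| f | Missed by the questionnaire, 88 × 0.148 × f | Per arm, 44 × 0.148 × f |
|---|---|---|
| 0 | 0 | 0 |
| 0.25 | 3.3 | 1.6 |
| 0.50 | 6.5 | 3.3 |
| 0.75 | 9.8 | 4.9 |
| 1 | 13.0 | 6.5 |

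These are upper limits on what is lost altogether, because general monitoring may catch some events that start during the Toolbox.

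**Effect on the arm comparison.** If the true rates are pA and pS and the same share f is missed in each arm, the recorded rates are pA(1 − f) and pS(1 − f). The ratio is unchanged, and the absolute difference shrinks by the factor 1 − f. There is less information, but no spurious difference is created. A spurious difference would require f to differ by arm, and nothing in the documents suggests that.

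**The case against.** Much can fairly be said for the plan. The questionnaire follows stimulation, so redness, pain, headache or dizziness present by then is recorded. Appendix C describes several of these effects as short-lived and headache as usually settling soon, so many may fall within the visit. Monitoring for the whole visit covers the Toolbox period. The randomized arms share the same window. All of this stands, and it rules out four stronger readings that a reader might infer.

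- *That the questionnaire precedes the Toolbox and uses up the rest break.* This is an inference from a table column, a stated duration and a footnote. Figure 2, which the text cites for this session, could not be seen and may show the order.
- *That after-effects cannot be counted at all.* This is true only at f = 1, which nothing in the documents supports.
- *That the active-sham comparison is biased.* Both arms lose the same window.
- *That the 5-day cohort is fully covered by contrast.* The recall period of the daily questionnaire is not given, so its capture of overnight events is assumed. The 1-month visit has no adverse-event mark in the 5-day schedule, although the general rule would require one. No adverse-event comparison between the 1-day and 5-day cohorts is planned.

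The objection does not reach events that start after the participant leaves: no part of the plan collects them. General monitoring is also not said to feed the planned comparison.

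There is also a sound objection to simply moving the one questionnaire to the end of the visit. Participants, half of them with MCI, would then have to recall sensations from about 35 minutes earlier, including itching and tingling, the most frequent effects cited in Appendix C.

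**Conclusion.** The concern holds in a limited form. For 88 of 132 participants, adverse events that start after the single visit have no planned collection. Those that start after the questionnaire but within the visit depend on general monitoring whose place in the analysis is not stated. Absolute rates of the after-treatment effects named in Appendix C would therefore be under-counted in both arms, to the extent that they start late.

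How much is lost cannot be derived from the documents. The range of 0 to about 13 headaches assumes that the cited 14.8% applies to both arms and to both 1-day cohorts, and it includes no loss. The finding does not depend on the order of questionnaire and Toolbox; that order is simply unspecified. The documents do not support a claim that the arm comparison is biased or that after-effects go wholly unrecorded.

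**What to change.** - Keep the questionnaire after stimulation, so that sensations during treatment are recorded while fresh.
- Mark adverse-event monitoring under Post-Intervention in the 1-day schedule, and repeat the same questionnaire at the end of the visit, after the NIH Toolbox.
- Add one brief telephone repeat the next day for 1-day participants, made by existing staff.
- Report the three time points separately by arm.
- Reconcile the 1-day schedule and its text, the general rule under Risks and Adverse Events, Appendix C's list of effects following treatment, and the Participant Safety item of the Data and Safety Monitoring Plan. State the order of questionnaire and Toolbox, and whether events noted by general monitoring enter the arm comparison.

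The cost is about 5 more minutes at the visit and one call of about 5 minutes per participant. The calls total 88 × 5 = 440 minutes, or roughly 7 hours over the study.
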